### 13.4 Repeat Ablation Procedures

Repeat procedures may be performed at the discretion of the investigator. It is highly recommended to collect arrhythmia documentation (in example documented recurrences) before performing a repeat procedure.

#### During the blanking period:

- Repeat procedures during the blanking period ( $\leq 90$  days post index ablation procedure) must be conducted with the investigational device, with or without focal touch-up, if the arrhythmia is due to PV triggers. ONLY after investigator deems unable to achieve PVI with the investigational device, a commercial and compatible BWI (RF) system can be used to complete the procedure (PVI only).
- If the arrhythmia is due to non-PV triggers and the subject is treated with a commercially available ablation catheter and generator, the subject will be excluded from the long-term effectiveness cohort.
- Procedures for newly CTI dependent flutter in the follow up period are not considered repeat procedures per CIP and will be treated with a commercially available ablation catheter and generator.

#### After the Blanking period:

Repeat procedures performed after the blanking period (91- 365 days post index ablation procedure) may be managed per investigator discretion using a commercially available ablation catheter and generator.

For the repeat procedures, the investigator must collect and provide information on location of reconnections of PVs and in case of atrial flutter recurrence, confirm if CTI dependent flutter or not. The follow-up schedule will remain based on the index ablation procedure.

### 13.5 Post-Ablation Follow-up Schedule

The subjects will be required to complete follow-up visits through 12 months post index ablation procedure. Follow-up will be done at 7 days (phone call or clinic visit), 1, 3, 6 and 12 months (clinic visit). Follow-up visits should be scheduled according to the following timeframes: 1 month (1M 23-37), 3 months (3M, day 76-104), 6 months (6M, day 166-194) and 12 months (12M, day 335-379). Follow-up visit schedule should be based on the date of the index ablation procedure and will not reset if subject undergoes a repeat AF ablation procedure.

#### 13.5.1 Seven (7) day follow-up visit

Discharged subjects will receive a **telephone call** or have a clinic **visit** at 7 days (7d, day 7-9) post ablation procedure to assess any occurrence of **Adverse Events** and any change in **medication regimen**. If subject is coming for a clinic visit at day 7, data from 12 lead ECG will be collected.

### 13.5.2 Monthly follow-up visit

At 1, 3, 6 and, 12-month follow-up visits, the following assessments will be performed:

- **Medical evaluation:**
  - AEs
  - Cardiac and anti-coagulation medication regimen
  - Cardiac related hospitalization and cardioversions
  - 12 Lead-ECG
  
- **As from 1-month: Atrial arrhythmia monitoring (non-SOC)**
  - **Remote Monitoring:** subjects will be provided with a remote monitoring device at the 1M FU visit and asked to record and transmit a minimum of 1 transmission ( $\geq 30$  seconds) every week through the end of the month 5 of FU. Starting at month 6 of FU, subjects will be asked to record and transmit a minimum of 1 transmission ( $\geq 30$  seconds) every month until the effectiveness evaluation period is completed (12 months post index ablation procedure). Subjects will also be asked to transmit any symptom-triggered episode that occurs from the time they receive the remote monitoring device through the 12M FU visit. Remote monitoring will be **conducted as follows:**
    - Distribution and start by month 1.
    - $<6M$ : Weekly transmission of at least 1 scheduled recording.
    - $\geq 6M$ : Monthly transmission of at least 1 scheduled recording.
    - Conduct and transmit recording whenever symptoms are present.
  - **24 Hour Holter Monitoring:** per CIP a Holter monitor will be used at the 3-, 6- and 12-months follow-up visit to monitor the subjects 'heart rhythm for 24 hours continuously. Following the 24h Holter, subjects will be contacted by the site to verify if symptoms are experienced during 24h Holter. An independent core laboratory will be used to evaluate and assess the remote and 24h Holter monitoring tracings.
  
- Additional Assessments for Cardiac **CT/MRA** subset subjects: A **cardiac CT/MRA** is required to be performed at the 3M FU (non-SOC) visit or any other point in time when the subject presents with symptoms of PV stenosis. For other subjects, a cardiac CT/MRA is only required to be performed if the subject presents with symptoms of PV stenosis.
  
- Additional Assessments for **NA** subset subjects (non-SOC): A **Cerebral MRI, Neurological Exam and Neurological Evaluation using the MMSE, NIHSS and mRS** are required to be performed if any neurological symptoms and/or cerebral ischemic lesions were identified at a prior evaluation. NOTE: Patient questionnaires will only be used in countries with validated languages.
  
- Additional Assessments for **PVI Durability subset** subjects (non-SOC):
  - A repeat electro anatomical creation of a paced activation map and bipolar voltage map will be performed at 75 days (+/-15days) post index ablation procedure to verify isolation durability of the treated pulmonary vein during the index ablation procedure.
  - A BWI multi-electrode mapping catheter should be used for the remap procedure. It is **REQUIRED** to use the same mapping catheter that was used during the index ablation procedure.
  - If reconnections are identified in the remap procedure, additional ablations may be performed at the discretion of the investigator with the investigational ablation system. If the additional ablations cannot be achieved with the investigational system, a commercially approved and compatible BWI RF catheter and generator should be used.

- **Quality of life** via the Atrial Fibrillation Effect on Quality-of-Life (AFEQT™) questionnaire (non-SOC), at Month 3, 6 and 12. NOTE: Patient questionnaires will only be used in countries with validated languages.

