### **7.4.2 Secondary Hypothesized Endpoints**

#### **12-Month Effectiveness**

Freedom from documented (symptomatic and asymptomatic) atrial arrhythmia (AF, AT or AFL of unknown origin\*) episodes based on electrocardiographic data ( $\geq 30$  seconds on arrhythmia monitoring device) during the effectiveness evaluation period (day 91-day 365) on or off antiarrhythmic therapy. Acute procedural failure (i.e., failure to achieve entrance block with the study device in any of the clinically relevant targeted PVs) will also be deemed a 12-month effectiveness failure.

*\*AFL of unknown origin is defined as all AFL except those CTI dependent AFL as confirmed by 12-lead electrocardiogram (ECG) or entrainment maneuvers in an EP study.*

Further refer to Appendix 1 for definitions on effectiveness terms.

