The main study will enroll 135 evaluable subjects who have symptomatic PAF and are candidates for atrial fibrillation ablation. To minimize the learning curve effect on the evaluation of safety and effectiveness of the OMNYPULSE™ Bi-Directional Catheter, up to 50 Roll-In subjects will be enrolled in the study. These subjects will not be counted in the main study, and data for Roll-In subjects will be analyzed separately from the main study.

During the study, all subjects will be followed for 12 months after index procedure. All subjects will be evaluated at 7 days (Day 7-9), 1 month (Day 23-37), 3 months (Day 76-104), 6 months (Day 166-194), and 12 months (Day 335-379) following the index ablation procedure (Day 0).

The primary safety and effectiveness endpoint will be evaluated using the data available at the time of the 3-month follow-up. The hypothesis testing of the primary endpoints will be performed when all subjects complete their 3-month follow-up. A Clinical Study Report (hereinafter, 3-Month CSR) will be submitted as part of the CE mark application dossier.

After the 3-Month CSR submission, the primary safety and primary effectiveness endpoints, along with associated sensitivity analyses, may be summarized descriptively using the complete follow-up data, if there are any updates on the primary endpoint outcome data. No hypothesis testing will be conducted for the primary endpoints in the final CSR.

Regarding all other study endpoints, they will be summarized descriptively using the full follow-up data. The final analysis results will be compiled and presented in the Final CSR (hereinafter, Final CSR).

Embedded within the main study, there will be a Neurological Assessment (NA) subset, a cardiac Computed Tomography (CT) or Magnetic Resonance Angiogram (MRA) image subset, an Esophageal Endoscopy (EE) subset, and a Pulmonary Vein Isolation (PVI) durability subset. These subsets are intended to delineate safety and assess lesion durability 2-3 months following ablation. Each subset will consist of 30 subjects. The same subjects may participate in all four (4) subsets.

2 Treatment Assignment

This is a single-arm study. All subjects will be treated with the OMNYPULSE™ Bi-Directional Catheter (D-1430-05-SI) and the TRUPULSE™ Generator (D-1417-01-IC), along with any related components and accessories needed for the ablation procedure.

3 Randomization and Blinding Procedures

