7.4.3 Secondary Effectiveness Endpoint

The secondary effectiveness endpoint is 12-month effectiveness success, which is defined as freedom from documented (symptomatic and asymptomatic) atrial arrhythmia episodes including atrial fibrillation (AF), atrial tachycardia (AT), or atrial flutter (AFL, of unknown origin*). The AF/AT/AFL episodes will be assessed based on the electrocardiographic data (≥ 30 seconds on arrhythmia monitoring device) during the effectiveness evaluation period (91-365 days post the index procedure). Acute procedural failure (i.e., failure to achieve entrance block with the study device in any of the clinically relevant targeted PVs) will also be deemed a 12-month effectiveness failure. The secondary effectiveness success rate will be compared against a performance goal of 50%.

The hypotheses to be tested for this evaluation are:

$$H_0: P_{12m} \leq 0.50 \text{ vs. } H_A: P_{12m} > 0.50,$$

where P_{12m} denotes the proportion of subjects who are failure-free at 12 months follow-up.

**AFL of unknown origin is defined as all AFL except those CTI dependent AFL as confirmed by 12-lead electrocardiogram (ECG) or entrainment maneuvers in an EP study.*

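### Symptom-triggered remote recording is explicitly required only up to the 12-month visit, which is in window from Day 335, while the effectiveness period and the scheduled transmissions run to Day 365 or 12 months

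*Protocol*

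**What the plan says.** Protocol 13.5.2 describes two streams of remote recording and ends them differently. From month 6, subjects make at least one scheduled transmission "every month until the effectiveness evaluation period is completed (12 months post index ablation procedure"). For symptoms, they are asked to transmit "any symptom-triggered episode that occurs from the time they receive the remote monitoring device through the 12M FU visit". The bullet list that follows adds "Conduct and transmit recording whenever symptoms are present" with no end date. Footnote 7 to Tables 1 and 4 likewise asks for recordings on symptoms and gives no end.

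The 12-month visit is a window and not a fixed day: "12 months (12M, day 335-379") in Protocol 13.5, and "12 months (Day 335-379) following the index ablation procedure (Day 0") in SAP section 1. Tables 1 and 4 show D365 as its nominal day.

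The tested 12-month endpoint counts episodes "during the effectiveness evaluation period (day 91-day 365) on or off antiarrhythmic therapy" (Protocol 7.4.2), and SAP 7.4.3 has the same period: "during the effectiveness evaluation period (91-365 days post the index procedure"). Single procedural success and freedom from symptomatic arrhythmia (Protocol 7.4.3, SAP 7.4.5) also run from Day 91 to Day 365. The 24-hour Holter is tied to the 3-, 6- and 12-month visits.

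**The concern.** One paragraph sets two stopping rules for the same device. A subject seen on Day 335 can reasonably be told that symptom recording is finished, although the endpoint stays open for another 30 days. In those days the planned monitoring is sparse: scheduled transmissions need be no more than one recording of at least 30 seconds a month, and the last Holter has already been done at the early visit.

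Symptom-triggered recording is therefore the main planned means of documenting a symptomatic episode after an early visit. If it stops, either such episodes go undocumented, which would tend to raise the freedom rates, or the subject is censored at the visit and follow-up is lost. Which of the two applies cannot be checked, because the SAP text on missing data for this endpoint (7.8.3) and parts of 7.1 and 7.10 are redacted. Two additional endpoints are defined by symptomatic episodes, so they depend most on this stream. In either case, how long a subject is observed for symptoms would depend on when the visit was booked.

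**Working it through.** The plan states no figure for this gap, so there is none to reproduce.

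**Inputs from the documents**
- 12-month visit window: Day 335 to Day 379 (Protocol 13.5, SAP section 1), so 379 − 335 + 1 = 45 compliant days.
- Evaluation period: Day 91 to Day 365 (Protocol 7.4.2, SAP 7.4.3), so 365 − 91 + 1 = 275 days.
- Explicit end of symptom-triggered transmission: the 12-month visit (Protocol 13.5.2).

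**Days not covered**, counting the visit day as covered: g = max(0, 365 − visit day).

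| Visit day | g | Share of 275 days |
|---|---|---|
| 335 | 30 | 10.9% |
| 350 | 15 | 5.5% |
| 364 | 1 | 0.4% |
| 365 to 379 | 0 | 0% |

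Thirty of the 45 compliant days (335 to 364) leave a gap. If visits were spread evenly over the window (an assumption), the mean gap would be (30 + 29 + … + 1)/45 = 465/45 = 10.3 days, or 3.8% of the period.

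**Failures that could fall in the gap.** The documents give no usable 12-month freedom rate (the sample-size text is redacted), so freedom S is assumed to be 50%, 65% or 80%, with a constant hazard over the period:
- h = −ln(S)/275
- failures arising in the last g days = S × (exp(g·h) − 1)

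| Assumed S | h per day | All subjects seen on Day 335 (g = 30) | Visits evenly spread (mean over 45 days) |
|---|---|---|---|
| 50% | 0.00252 | 3.9 points | 1.3 points |
| 65% | 0.00157 | 3.1 points | 1.1 points |
| 80% | 0.00081 | 2.0 points | 0.7 points |

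The last column is an upper bound on what would be missed under even spread. It treats every failure as detectable only by symptom-triggered recording. In fact the tested endpoint includes asymptomatic episodes, which this stream does not target, and other monitoring would detect some of the rest.

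**Against the test.** As a rough guide with n = 135 and a simple binomial, freedom of 65% has a standard error of √(0.65 × 0.35/135) = 4.1 points and a lower 95% limit of about 65 − 1.96 × 4.1 = 57%. A shift of about one point leaves that well above 50%. With an exact interval, 80 of 135 (59.3%) is the fewest successes whose lower limit exceeds 50%, so a shift of this size could matter only near that boundary.

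**After the change.** With symptom-triggered transmission running to at least Day 365, g = 0 for every compliant visit date.

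**The case against.** The strongest reply is that the protocol can be read as having no gap. The bullet in 13.5.2 and footnote 7 ask for recordings whenever symptoms occur, without an end. Scheduled transmissions run to 12 months, so the subject evidently keeps the device, and nothing says it is handed back at the visit. The nominal day of the 12-month visit is D365, so the phrase about that visit could be meant as Day 365. Unscheduled visits for a new or worsened cardiovascular condition are also allowed, and the schedule marks ECG, remote monitoring and Holter for them (Protocol 13.7, Tables 1 and 4).

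Much of this stands, and it rules out a stronger reading. A reader might infer that the 12-month claim rests on less than 12 months of monitoring. The documents do not support that: scheduled monitoring continues to 12 months, and only the symptom-triggered stream has the earlier explicit end. A reader might also infer that the Kaplan-Meier estimates are biased upward. That cannot be said. Kaplan-Meier with non-informative censoring at last observation handles unequal follow-up, and the censoring rule is redacted, which is not itself a fault.

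The reply does not remove the inconsistency. The visit is the only explicit end given for symptom-triggered transmission, it can fall 30 days before the period closes, and sites may apply different readings.

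**Conclusion.** The point holds as a minor inconsistency in data collection. By its only explicit end, the rule allows symptom-triggered recording to stop up to 30 of 275 evaluation days (10.9%) early, and 30 of the 45 compliant visit days leave some gap. Visits on Day 365 or later leave none.

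The effect is small. At most about 0.7 to 1.3 percentage points of failures fall in the gap, assuming evenly spread visits, a constant hazard and 12-month freedom of 80% down to 50%. If visits clustered early the figure would be higher, up to 2.0 to 3.9 points if every subject were seen on Day 335. If they clustered around or after Day 365 it would be close to zero. The test against 50% is unlikely to change. The gain from correcting the text is that symptom-based observation covers the same period in every subject, which matters most for the two symptomatic endpoints. Neither of those carries a formal hypothesis.

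**What to change.** In Protocol 13.5.2, change the end of symptom-triggered transmission from the 12-month visit to at least Day 365, the end of the effectiveness evaluation period, and say that this applies even if the visit takes place earlier. This brings it into line with the adjacent sentence on scheduled transmissions, which needs no change. State the same end in footnote 7 of Tables 1 and 4.

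The cost is a change of phrase in 13.5.2 and in the footnote. Subjects seen before Day 365 keep using the device for up to 30 more days, which the scheduled transmissions already imply. No visit, test or analysis is added.

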76. Deshmukh, A., et al., *In-hospital complications associated with catheter ablation of atrial fibrillation in the United States between 2000 and 2010: analysis of 93 801 procedures*. Circulation, 2013. **128**(19): p. 2104-12.
77. Stewart, M.T., et al., *Intracardiac pulsed field ablation: Proof of feasibility in a chronic porcine model*. Heart Rhythm, 2019. **16**(5): p. 754-764.
78. Hindricks, G., et al., *2020 ESC Guidelines for the diagnosis and management of atrial fibrillation developed in collaboration with the European Association for Cardio-Thoracic Surgery (EACTS): The Task Force for the diagnosis and management of atrial fibrillation of the European Society of Cardiology (ESC) Developed with the special contribution of the European Heart Rhythm Association (EHRA) of the ESC*. Eur Heart J, 2021. **42**(5): p. 373-498.
79. Sugrue, A., et al., *Irreversible electroporation for catheter-based cardiac ablation: a systematic review of the preclinical experience*. J Interv Card Electrophysiol, 2019. **55**(3): p. 251-265.
80. Marijon, E., et al., *Real-time contact force sensing for pulmonary vein isolation in the setting of paroxysmal atrial fibrillation: procedural and 1-year results*. J Cardiovasc Electrophysiol, 2014. **25**(2): p. 130-7.
81. Cronin, E.M., et al., *2019 HRS/EHRA/APHS/LAHR expert consensus statement on catheter ablation of ventricular arrhythmias*. Heart Rhythm, 2020. **17**(1): p. e2-e154.

## 29 Appendix 1

Definitions on effectiveness terms are mentioned below.

Term	Definition
Recurrent AF/AT/AFL	Recurrent AF/AFL/AT is defined as AF/AFL/AT of at least 30 seconds' duration that is documented by an ECG or device recording system and occurs following catheter ablation. Recurrent AF/AFL/AT may occur within or following the post ablation blanking period. Recurrent AF/AFL/AT that occurs within the post-ablation blanking period is not considered a failure of AF ablation.
Early recurrence of AF/AFL/AT	Early recurrence of AF/AFL/AT is defined as a recurrence of atrial fibrillation within three months of ablation. Episodes of atrial tachycardia or atrial flutter should also be classified as a "recurrence." These are not counted toward the success rate if a blanking period is specified.

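### A compliant 3-month Holter can lie wholly in the blanking period (14 of 29 start days), so whether it contributes to the Day 91-365 endpoint depends on the appointment date

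*Protocol*

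**What the plan says.** - **Holter schedule.** Protocol 13.5.2: "per CIP a Holter monitor will be used at the 3-, 6- and 12-months follow-up visit", each recording the "heart rhythm for 24 hours continuously". Tables 1 and 4 place the Holter at the same three visits.
- **Visit timing.** Tables 1 and 4 give Day 90 as the study day of the 3-month visit and Day 76-104 as its window. Protocol 13.5 and SAP section 1 repeat the window, and the SAP counts the index procedure as Day 0.
- **Endpoint period.** Protocol 7.4.2 counts atrial arrhythmia episodes "during the effectiveness evaluation period (day 91-day 365) on or off antiarrhythmic therapy". SAP 7.4.3 uses the same days.
- **Blanking.** Protocol 7.4.3 and 13.4 take the blanking period as up to and including 90 days. Appendix 1 adds: "Recurrent AF/AFL/AT that occurs within the post-ablation blanking period is not considered a failure of AF ablation".
- **Other rhythm monitoring.** Under Protocol 13.5.2, remote recordings of at least 30 seconds are sent at least weekly from month 1 to the end of month 5 and at least monthly from month 6, plus whenever symptoms occur. A 12-lead ECG is taken at each clinic visit.
- **Test.** Protocol 19.8.3 compares the lower limit of the two-sided 95% Kaplan-Meier interval with 50% in the per-protocol set, and only if both primary endpoints are met.

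No visible text asks for the 3-month Holter to be recorded on or after Day 91.

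**The concern.** The endpoint includes asymptomatic episodes, which symptom-triggered transmissions do not find. The 24-hour Holter is the only scheduled continuous recording after discharge. Its first use is tied to a visit centred on the last day of blanking, so a subject can comply fully and still have a first Holter that is unable to show a failure.

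Two things follow. First, the effect has one direction. A recurrence that goes undetected leaves the subject counted as a success, and in a single-arm comparison with a fixed goal there is no control arm in which the same loss would cancel. Second, ascertainment differs between equally compliant subjects, and possibly between sites, according to when the appointment was made.

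The documents do adjust this boundary for another criterion. For antiarrhythmic drugs, Appendix 1 starts the assessment at the later of Day 91 and the visit day, and SAP 7.4.5 and 7.11.3 start it at Day 105, the day after the 3-month window closes. Nothing comparable is visible for the Holter.

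**Working it through.** **Step 1. The window.** 104 - 76 + 1 = 29 calendar days, which is Day 90 plus or minus 14 and agrees with Tables 1 and 4.

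**Step 2. Where a 24-hour recording falls.** A recorder fitted during day d runs into day d + 1.

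| Start day | Number of days | Position of the recording |
|---|---|---|
| 76-89 | 89 - 76 + 1 = 14 (14/29 = 48%) | wholly in blanking |
| 90 | 1 | partly in blanking, partly Day 91 |
| 91-104 | 104 - 91 + 1 = 14 (48%) | wholly in the evaluation period |

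**Step 3. What remains for a subject recorded on Day 76-89.** Two scheduled Holters are left. The 6-month window (Day 166-194) lies wholly inside Day 91-365. The 12-month window (Day 335-379) itself runs past Day 365, which is a separate matter and is not counted here.

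Scheduled remote recordings after Day 90 number roughly 15 to 20. If weekly sending stops at about Day 150, there are 60/7 = 8.6 weekly recordings; if it lasts to about Day 180, there are 90/7 = 12.9. About 7 monthly recordings follow, giving 15.6 or 19.9. At the 30-second minimum that is about 8 to 10 minutes in all, against 24 x 60 = 1,440 minutes for one Holter. Recordings may be longer or more frequent than the minimum.

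**Step 4. Possible size.** The documents give none of the rates needed, so all three inputs are assumptions: the share of subjects with recurrence that all other monitoring misses (m), the chance that one 24-hour Holter would catch it (y), and visits spread evenly over the 29 days, so that 14/29 of Holters are wholly lost. Expected missed failures = 135 x m x y x 14/29.

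- Middle: 135 x 0.10 x 0.20 x 14/29 = 1.3 subjects (1.3/135 = 1.0 percentage point)
- Low: 135 x 0.05 x 0.10 x 14/29 = 0.3
- High: 135 x 0.15 x 0.30 x 14/29 = 2.9

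The partial loss on Day 90 is left out.

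**Step 5. Scale against the goal.** With 135 subjects and an exact binomial test, 80 successes is the smallest number whose exact 95% lower limit exceeds 50% (0.505; 79 gives 0.497). This is an illustration only. The planned test is the Kaplan-Meier lower limit in the per-protocol set, with censoring for some uses of a commercial RF device, and the definition of that set is redacted.

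**The case against.** The strongest reply is that this is a scheduling choice and not a contradiction. The plan monitors rhythm during blanking on purpose: remote recording starts at month 1, and Appendix 1 defines early recurrence. A Holter on Day 76-90 serves that purpose, and no text says that the 3-month Holter exists only for the tested endpoint. That stands, and the point is therefore a cheap improvement and not an error.

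The reply also notes that the weeks just after Day 91 have the densest scheduled remote recording of the whole evaluation period, and that a subject whose arrhythmia continues has later chances to be found. This stands too. The loss concerns asymptomatic recurrence that short recordings and the later Holters both miss.

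Parts of the SAP conventions and of the secondary analysis are redacted, so a handling rule may exist there. Such a rule could say how a recording is classed, but it could not supply a recording after Day 90 that was never made.

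Three stronger readings are tempting, and the documents support none of them:

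- A reader might infer that the Holter is lost on 15 of 29 days, including the target day. A recorder fitted on Day 90 runs into Day 91, so that day is lost only in part.
- A reader might infer that about half of subjects lose their first Holter. The figure is a share of compliant days, and the documents give no distribution of visit dates.
- A reader might infer that the result against 50% turns on this. The sample-size inputs are redacted, and nothing visible places the expected rate near the goal.

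**Conclusion.** The mismatch is real and follows from the calendar alone: 14 of 29 compliant start days put the first Holter wholly outside the period that counts, and one more puts it partly outside. Compared with a recording made on or after Day 91, this lowers detection of asymptomatic recurrence, can move the tested success rate only upward, and makes ascertainment depend on the appointment date.

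The size is probably small, about 1 subject and at most about 3 of 135 over the assumed ranges, and it would matter only for a result close to the limit. That estimate rests entirely on the assumed missed-recurrence rate, the assumed Holter yield and an even spread of visits. The endpoint is a gated secondary one and neither primary endpoint is affected. The case for a change rests on the one-way direction and the low cost, not on the estimated size.

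**What to change.** Keep the 3-month visit window as it is. Add to Protocol 13.5.2, and as a footnote to Tables 1 and 4, that the 24-hour recording used for the 12-month endpoint starts on or after Day 91. Day 91-104 already lies inside the window, so no test is added.

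If the 3-month visits are already complete, report in the final study report how many 3-month Holters were recorded on or after Day 91, so that a reader can judge how much continuous monitoring supported the estimate.

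The cost is protocol wording and appointment planning. The usable Holter window narrows from 29 to 14 days. Subjects seen before Day 91 would start the recorder after the visit, by up to about two weeks (91 - 76 = 15 days at most), with some risk of missed recordings and of more protocol deviations. Booking the visit for Day 91-104 where possible limits that risk.
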